4.2. SECONDARY EFFICACY ENDPOINTS

The secondary endpoints are the following:

1. Percentage of subjects with a CAS value of 0 or 1 in the study eye at Week 24.
2. Mean change from Study Baseline to Week 24 in proptosis measurement in the study eye.
3. Diplopia responder rate (percentage of subjects with Study Baseline diplopia >0 in study eye who have a reduction from Study Baseline of ≥ 1 grade with no corresponding deterioration [≥ 1 grade worsening] in the fellow eye) at Week 24.
4. Mean change from Study Baseline to Week 24 in the GO-QoL questionnaire overall score.

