6.3.5. Efficacy Assessments

For the binary primary and secondary endpoints, subjects missing the evaluations at a given visit will be treated as failures (non-responders). No imputation of missing data will be performed for any continuous efficacy assessments.

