8.2. SECONDARY EFFICACY ENDPOINTS AND ANALYSES

8.2.1. CAS Categorical Response

The CAS will be completed at Day 1 and Weeks 6, 12, 18, and 24 (or PW) during the Treatment Period, and for HZNP-TEP-301 non-responders at Weeks 28, 36, 48 (or PW) in the Follow-Up Period using the 7 item European Group on Graves' Ophthalmopathy (EUGOGO) amended CAS (Mourits et al, 1989) for each eye.

For each item present, one point is given. The sum of these points is the total score.

- Spontaneous orbital pain
- Gaze evoked orbital pain
- Eyelid swelling that is considered to be due to active (inflammatory phase) TED/GO
- Eyelid erythema
- Conjunctival redness that is considered to be due to active (inflammatory phase) TED/GO (ignore "equivocal" redness)
- Chemosis
- Inflammation of caruncle or plica

The first secondary endpoint is CAS as a categorical response variable defined as a reduction to a CAS of 0 or 1 from Study Baseline at Week 24. Subjects missing the Week 24 evaluation will be considered to be treatment failures (non-responders) for the analysis. Descriptive summaries of responder results will be provided for the study eye and fellow eye by treatment received in HZNP-TEP-301 for the ITT Population at Week 24. Only subjects with CAS > 1 at study baseline in the ITT Population will be summarized.

In addition, descriptive summaries of responder results will be provided for the study eye and fellow eye by treatment received in HZNP-TEP-301 for the ITT Population for each visit in the Treatment Period and for HZNP-TEP-301 proptosis non-responders in the Follow-Up Period, considering subjects missing the evaluations as treatment failures (non-responders). Similar summaries will also be provided separately by subject enrollment type (subjects who were proptosis non-responders in HZNP-TEP-301, subjects who relapsed during the Follow-Up Period in HZNP-TEP-301), tobacco use status (non-user, user), region (US, EU), and site. The proportion of subjects with a complete CAS response (subjects who have a CAS of 0) in the study eye will be summarized for each visit in the Treatment Period and Follow-Up Period considering observed results only. Only subjects with CAS > 0 at study baseline in the ITT Population will be summarized.

Summaries after Week 24 for subjects who were proptosis non-responders in HZNP-TEP-301, will also include a summary of sustained CAS response, where sustained responder

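### Complete CAS response (CAS 0) is summarised on observed cases and a wider baseline set than CAS 0/1, so the two rates are not comparable and the stricter one can come out higher

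*SAP*

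**What the plan says.** The listed secondary endpoint in SAP 4.2 is: "Percentage of subjects with a CAS value of 0 or 1 in the study eye at Week 24". SAP 8.2.1 handles missing data for it in two places. At Week 24: "Subjects missing the Week 24 evaluation will be considered to be treatment failures (non-responders) for the analysis". For the by-visit summaries, with Follow-Up limited to subjects who were proptosis non-responders in HZNP-TEP-301, the phrase is "considering subjects missing the evaluations as treatment failures (non-responders"). The denominator is restricted by baseline score: "Only subjects with CAS > 1 at study baseline in the ITT Population will be summarized".

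The same section then adds complete CAS response, meaning a study-eye score of 0. It is summarised at each visit in the Treatment "Period and Follow-Up Period considering observed results only", with a different baseline restriction: "Only subjects with CAS > 0 at study baseline in the ITT Population will be summarized". This sentence does not limit Follow-Up to the lead-in non-responders. The result is Table 14.2.2.6, labelled ITT. Complete CAS response is not among the endpoints in SAP 4.1 to 4.3.

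The general rule in SAP 6.3.5 reads: "For the binary primary and secondary endpoints, subjects missing the evaluations at a given visit will be treated as failures (non-responders"). SAP 12, on changes from the protocol, does not mention the different treatment of CAS 0.

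**The concern.** Every subject at CAS 0 is also at CAS 0 or 1, so a reader expects the complete-response rate to be the lower of the two. The plan does not guarantee that, because the two rates differ in both missing-data rule and baseline set. The tables will sit side by side, and a complete-response figure is likely to be quoted.

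The missing subjects need not resemble the rest. Protocol 9.3.3 allows removal for lack of efficacy and withdrawal to receive other TED treatment. Under SAP 6.4 a premature-withdrawal visit is assigned only to its nearest scheduled visit. A subject who leaves early and does not continue is therefore a failure for CAS 0/1 at later visits but drops out of the CAS 0 denominator.

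**Working it through.** **No figure to reproduce.** SAP 3.5 says that the sample size has no statistical basis, and the documents give no CAS response or dropout rate. All counts below are assumptions.

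**Where CAS 0 stands among the responder proportions.** Missing counts as non-response for proptosis response and its sustained form (8.1), CAS 0/1 and its sustained form (8.2.1), diplopia response and its three follow-up outcomes (8.2.3), overall response and its sustained form (8.3.1), the Clinical Measures of Severity items (8.3.2.1) and the four-category response (8.3.4). The closest parallel is the no-diplopia outcome in 8.2.3. It too is a supportive outcome requiring a score of 0 and is not a listed endpoint, yet missing counts as failure. Supportive status alone does not explain the exception.

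**Notation.** N subjects in the summary, m missing at the visit, r01 observed at CAS 0 or 1, r0 observed at CAS 0 (r0 ≤ r01).

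**Effect of the missing-data rule, common baseline set.**
- CAS 0/1 as planned: r01/N.
- CAS 0 as planned: r0/(N − m). With missing as failure: r0/N.
- Ratio of the two CAS 0 rates: N/(N − m), which is 1/0.95 = 1.05, 1/0.90 = 1.11 and 1/0.80 = 1.25 at 5%, 10% and 20% missing.
- CAS 0 exceeds CAS 0/1 when r0/(N − m) > r01/N, that is r0/r01 > 1 − m/N. The share of CAS 0/1 responders at CAS 0 must exceed 95%, 90% and 80% at 5%, 10% and 20% missing.

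Assume N = 40 and r01 = 28, so CAS 0/1 = 28/40 = 70.0%:

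| m | r0 | r0/r01 | 1 − m/N | CAS 0 as planned | CAS 0, missing = failure |
|---|---|---|---|---|---|
| 2 | 27 | 96.4% | 95% | 27/38 = 71.1% | 27/40 = 67.5% |
| 4 | 26 | 92.9% | 90% | 26/36 = 72.2% | 26/40 = 65.0% |
| 8 | 24 | 85.7% | 80% | 24/32 = 75.0% | 24/40 = 60.0% |
| 4 | 20 | 71.4% | 90% | 20/36 = 55.6% | 20/40 = 50.0% |

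The first three rows invert; the last does not. Under one rule the order is always right: in the third row, observed cases for both give 28/32 = 87.5% against 75.0%.

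**When the observed-case rate is too high.** Let q be the CAS 0 rate that the missing subjects would have shown. The full-set rate is (r0 + qm)/N, and the observed-case rate exceeds it by (m/N) × [r0/(N − m) − q]. This is positive only if the missing subjects do worse than those observed. In the third row it is 0.20 × (75% − q): 15 points too high at q = 0, nil at q = 75%, and 5 points too low at q = 100%.

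**Effect of the baseline set, no missing data.** Take 40 subjects with baseline CAS above 1, of whom 28 reach 0/1 and 27 reach 0, and add 6 with baseline CAS of 1 who all reach 0. CAS 0/1 is 28/40 = 70.0%; CAS 0 is (27 + 6)/(40 + 6) = 33/46 = 71.7%. With 26 instead of 27 it is 32/46 = 69.6%, with no inversion. The baseline sets are thus a second, independent route.

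**The case against.** The best defence is that the rule is deliberate and disclosed. SAP 14.2.5.2 makes subjects with an observation the default denominator for percentages and requires denominators to be footnoted. Complete CAS response is descriptive, no test rests on it, and the subject-level scores are listed. Missing-as-failure is itself a convention that can understate response. All of this stands, and it keeps the point small. It does not explain why this one responder proportion keeps the default when the no-diplopia outcome does not.

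A reader might infer more than the documents support:
- *That 8.2.1 contradicts 6.3.5.* It does not. The 6.3.5 rule is confined to binary primary and secondary endpoints. The departure is from the convention in the rest of section 8.
- *That CAS 0 will come out above CAS 0/1.* This is possible, not certain. With little missing data nearly all CAS 0/1 responders would have to be at CAS 0.
- *That the CAS 0 rate is known to be biased upward, and more so in Follow-Up.* The direction depends on how the missing subjects would have done, and no dropout rate is given for any period.

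The observed-case wording also does one useful thing. Relapse subjects have no Follow-Up clinic visits (SAP 3.4), and the CAS 0 sentence does not exclude them there. Simply swapping in missing-as-failure would count them as failures at visits that they never have.

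**Conclusion.** The concern holds as an unexplained inconsistency in one supportive table. As planned, the CAS 0 and CAS 0/1 rates differ in missing-data rule and baseline set, so they cannot be compared directly without reworking the denominators. With any missing data and any responder, the planned CAS 0 rate is higher than under the rule used for CAS 0/1, by a factor of about 1.05, 1.11 and 1.25 at 5%, 10% and 20% missing. It overstates the true rate only if missing subjects do worse, which the withdrawal provisions make plausible but the documents do not establish. The sizes rest on assumed counts and missing fractions. The primary endpoint and the listed CAS endpoint are unaffected, so this is a minor point, but a cheap one to settle.

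**What to change.** In SAP 8.2.1, three changes to the complete CAS response summary:
1. Count a missing evaluation as non-response at each Treatment Period visit and, for HZNP-TEP-301 proptosis non-responders only, at each Follow-Up visit. The restriction is needed so that relapse subjects are not counted as failures after Week 24.
2. Show the result also on the baseline CAS above 1 set used for CAS 0/1. With one rule and one set, r0 ≤ r01 rules out inversion; aligning the missing-data rule alone does not.
3. Keep the observed-case version as a labelled sensitivity summary, with its denominator stated.

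The cost is a short edit to 8.2.1 and a revised Table 14.2.2.6. No new data are needed. The downside for the sponsor is a slightly less favourable headline rate for complete response.

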8.2.2. Proptosis as a Continuous Variable

The second secondary efficacy endpoint is proptosis as a continuous variable. Descriptive summaries of observed proptosis as a continuous variable, change from Study Baseline and change from HZN-001 Baseline will be provided for the study eye and fellow eye by treatment received in HZNP-TEP-301 for the ITT Population at Week 24. In addition, descriptive summaries of observed proptosis as a continuous variable will be provided for the study eye and fellow eye by treatment received in HZNP-TEP-301 for the ITT Population for each visit in the Treatment Period and for HZNP-TEP-301 proptosis non-responders in the Follow-Up Period. Similar summaries will be provided separately by subject enrollment type (subjects who were proptosis non-responders in HZNP-TEP-301, subjects who relapsed during the Follow-Up Period in HZNP-TEP-301), tobacco use status (non-user, user), region (US, EU), and site.

A plot of mean change of proptosis value from Study Baseline by visits and treatment received in HZNP-TEP-301 will also be provided.

8.2.3. Diplopia Categorical Response

Diplopia will be assessed at Day 1 and Weeks 6, 12, 18, and 24 (or PW) during the Treatment Period, and for HZNP-TEP-301 proptosis non-responders at Weeks 28, 36, 48 (or PW) in the Follow-Up Period. The subjective diplopia score (0=no diplopia; 1=intermittent, i.e. diplopia in primary position of gaze, when tired or when first awakening; 2=inconstant, i.e. diplopia at extremes of gaze; 3=constant, i.e. continuous diplopia in primary or reading position) is recorded for each eye. A subject will be considered to have diplopia if a score > 0 is observed in the study eye at Study Baseline

(for summaries relative to Study Baseline) or HZN-001 Baseline (for summaries relative to HZN-001 Baseline).

The third secondary endpoint is diplopia responder. Only subjects with diplopia (diplopia > 0) in the study eye at Study Baseline (for summaries relative to Study Baseline) or HZN-001 Baseline (for summaries relative to HZN-001 Baseline) will be included in this analysis. A subject will be considered a responder if the grade of diplopia (scored from 0 to 3) decreases by at least one grade in the study eye without worsening by at least one grade in the fellow eye. Subjects with diplopia at baseline who are missing the Week 24 diplopia evaluation will be considered treatment failures (non-responders). Descriptive summaries of responder results will be provided for the study eye and fellow eye by treatment received in HZNP-TEP-301 for the ITT Population at Week 24.

In addition, descriptive summaries of responder results will be provided for the study eye and fellow eye by treatment received in HZNP-TEP-301 for the ITT Population for each visit in the Treatment Period and for HZNP-TEP-301 proptosis non-responders in the Follow-Up Period, considering subjects missing the evaluations as treatment failures (non-responders). Similar summaries will also be provided separately by subject enrollment type (subjects who were proptosis non-responders in HZNP-TEP-301, subjects who relapsed during the Follow-Up Period in HZNP-TEP-301), tobacco use status (non-user, user), region (US, EU), and site. Summaries after Week 24 for subjects who were proptosis non-responders in HZNP-TEP-301, will also include the following three endpoints:

- Sustained responder: of those subjects with diplopia at Study Baseline who were a diplopia responder at Week 24, the proportion who remained a diplopia responder at each post-Week 24 assessment (defined as having a diplopia score that decreases by at least one grade in the study eye without worsening of diplopia by at least one grade in the fellow eye) and did not receive any additional TED treatment by the time of the visit.
- Sustained 0: of those subjects with diplopia at Study Baseline who had a diplopia score of 0 at Week 24, the proportion who had a diplopia score of 0 at each post-Week 24 assessment (without worsening of diplopia by at least one grade in the fellow eye) and did not receive any additional TED treatment by the time of the visit.
- No diplopia: of those subjects with diplopia at Study Baseline regardless of the value at Week 24, the number with a diplopia score of 0 at each post-Week 24 assessment (without worsening of diplopia by at least one grade in the fellow eye) and did not receive any additional TED treatment by the time of the visit.

Additional TED treatment will include any instances of TED medication (identified by manual listing review), TED concomitant procedure (identified by manual listing review), TED surgical procedures, and/or orbital radiation treatments.

For each of these assessments, subjects who are missing diplopia values at a visit will be considered non-responders at that visit.

A plot of proportion of diplopia responder by visits and treatment received in HZNP-TEP-301 will also be provided.

8.2.4. GO-QoL Questionnaire Overall Score

For the fourth efficacy endpoint analysis, the GO-QoL questionnaire ([Terwee et al., 1998](#)) will be completed at Baseline, Weeks 6, 12, 24 (or PW) during the Treatment Period, and for HZNP-TEP-301 proptosis non-responders at Weeks 28, 48 (or PW) during the Follow-Up Period. The GO-QoL is a 16-item self-administered questionnaire divided into two subsets and used to assess the perceived effects of TED by the subjects on (i) their daily physical activity as it relates to visual function, and (ii) psychosocial functioning.

The sum of the scores from each set of eight questions will be calculated and transformed to a scale from 0 to 100 - one for visual function (VF), one for appearance (A) and one for the overall combined score. Scores will be transformed as follows:

Transformed score = $[(\text{sum of each score} - \text{number of completed items}) / (2 * \text{number of completed items})] * 100$.

Descriptive summaries of the transformed scores and change from Study Baseline will be provided by treatment received in HZNP-TEP-301 group for the ITT Population at Week 24.

In addition, descriptive summaries of the transformed scores will be provided by treatment received in HZNP-TEP-301 for the ITT Population at each visit in the Treatment Period and for HZNP-TEP-301 proptosis non-responders in the Follow-Up Period. Similar summaries will be provided separately by subject enrollment type (subjects who were proptosis non-responders in HZNP-TEP-301, subjects who relapsed during the Follow-Up Period in HZNP-TEP-301), tobacco use status (non-user, user), region (US, EU), and site.

A plot of mean change of GO-QoL overall transformed score from Study Baseline by visits and treatment received in HZNP-TEP-301 will also be provided.

8.3. EXPLORATORY EFFICACY ENDPOINTS AND ANALYSIS

8.3.1. CAS and Proptosis Categorical Response

The first exploratory efficacy endpoint is the overall responder rate, measured as the percentage of subjects with ≥ 2 -point reduction in CAS AND ≥ 2 mm reduction in

proptosis from Study Baseline, provided there is no corresponding deterioration (≥ 2 point/mm increase) in CAS or proptosis in the fellow eye at Week 24. Subjects missing the Week 24 evaluation will be considered to be treatment failures (non-responders) for the analysis. Only subjects with CAS > 1 and proptosis > 1 mm at Study Baseline in the ITT Population will be summarized.

Descriptive summaries of responder results for both study eye and fellow eye responder definitions will be provided by treatment received in HZNP-TEP-301 for the ITT Population at Week 24.

In addition, descriptive summaries of responder results for both study eye responder definitions (study eye responder and fellow eye responder) will be provided by treatment received in HZNP-TEP-301 for the ITT Population for each visit in the Treatment Period and for HZNP-TEP-301 proptosis non-responders in the Follow-Up Period, considering subjects missing the evaluations as treatment failures (non-responders). Similar summaries will also be provided separately by subject enrollment type (subjects who were proptosis non-responders in HZNP-TEP-301, subjects who relapsed during the Follow-Up Period in HZNP-TEP-301), tobacco use status (non-user, user), region (US, EU), and site.

Summaries after Week 24 for subjects who were proptosis non-responders in HZNP-TEP-301, will also include a summary of sustained CAS and proptosis response, where sustained responder is defined for subjects who were a responder at Week 24 and remained a responder post-Week 24 (defined as having ≥ 2 -point reduction in CAS AND ≥ 2 mm reduction in proptosis from Baseline, provided there is no corresponding deterioration (≥ 2 point/mm increase) in CAS or proptosis in the fellow eye) and did not receive any additional TED treatment by the time of the visit. Additional TED treatment will include any instances of TED medication (identified by manual listing review), TED concomitant procedure (identified by manual listing review), TED surgical procedures, and/or orbital radiation treatments. At each assessment after Week 24, the proportion of subjects who are sustained responders will be summarized by treatment received in HZNP-TEP-301. Subjects who are missing values at a visit will be considered non-responders at that visit.

A plot of proportion of overall responder by visits and treatment received in HZNP-TEP-301 will also be provided.

8.3.2. Clinical Measures of Severity

The following items, based on the EUGOGO Consensus Statement ([Bartalena et al, 2008](#); [Wiersinga et al, 2006](#)) will be assessed at Day 1, and Weeks 6, 12, 18, 24 (or PW) during the Treatment Period and for HZNP-TEP-301 non-responders at Weeks 28, 36, 48 (or PW) during the Follow-Up Period. Except when strictly unavoidable, the same observer should conduct each evaluation of severity measure for the full duration of the study.

8.3.2.1. Categorical Response Variables

[Table 2](#) provides a list of each Clinical Measures of Severity item and the assessment scale for classifying overall response.

Table 2: Clinical Measures of Severity

Clinical Measures of Severity Item and Assessment Scale	Minimum change required for classifying overall response
Exophthalmos (measured in mm using the same Hertel exophthalmometer and same intercanthal distance for each individual subject)	Decrease \geq 2 mm
Lid aperture (distance between the lid margins in mm with the subject looking in the primary position, sitting relaxed and with distant fixation)	Decrease \geq 2 mm
Swelling of the eyelids (absent, mild, moderate, severe)	Decrease \geq One grade
Redness of the eyelids (absent, present)	Decrease \geq One grade
Redness of the conjunctiva (absent, present)	Decrease \geq One grade
Conjunctival edema (absent, present)	Decrease \geq One grade
Inflammation of the caruncle or plica (absent, present)	Decrease \geq One grade
Subjective diplopia score (0=no diplopia; 1=intermittent, i.e. diplopia in primary position of gaze, when tired or when first awakening; 2=inconstant, i.e. diplopia at extremes of gaze; 3=constant, i.e. continuous diplopia in primary or reading position)	Decrease \geq One grade
Eye muscle involvement (ductions in degrees)	Increase \geq 8° in at least one direction of gaze
Corneal involvement (absent/punctate keratopathy/ulcer)	Decrease \geq One grade

Clinical Measures of Severity Item and Assessment Scale	Minimum change required for classifying overall response
Optic nerve involvement (best corrected visual acuity, color vision, optic disc, relative afferent pupillary defect (absent, present), and visual fields if optic nerve compression is suspected).	Change of best corrected visual acuity by ≥ 2 lines on Snellen chart, or substantial color vision change, or significant change of visual fields, or significant change in optic disc appearance, or (Dis-) appearance of relative afferent pupillary defect

Response is assessed individually for each item.

Subjects who have a Study Baseline assessment on a particular measure for which improvement is not possible (i.e. they have the best possible assessment) will be considered to be a responder if they maintain the Study Baseline assessment. The analysis of optic nerve involvement will be generated only if at least 10% of the subjects have optic nerve decompression.

The Clinical Measures of Severity results will be summarized for the study eye and fellow eye by treatment received in HZNP-TEP-301 for the ITT Population at Week 24, with the number and percentage of subjects being classified as responders on each individual item. Subjects missing the Week 24 evaluation will be considered to be treatment failures (non-responders) for the analysis. In addition, the Clinical Measures of Severity results will be summarized for each visit in the Treatment Period and for HZNP-TEP-301 proptosis non-responders in the Follow-Up Period for the study eye and fellow eye by treatment received in HZNP-TEP-301 for the ITT Population, with the number and percentage of subjects being classified as responders on each individual item and considering subjects missing the evaluations as treatment failures (non-responders).

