**Table 9.3 Clinical Measures of Severity**

Item and Assessment Scale	Minimum change required for classifying overall response
Exophthalmos (measured in mm using the same Hertel exophthalmometer provided by the Sponsor for consistency in measurement and same intercanthal distance for each individual patient)	Decrease $\geq$ 2 mm
Lid aperture (distance between the lid margins in mm with the patient looking in the primary position, sitting relaxed and with distant fixation)	Decrease $\geq$ 2 mm
Swelling of the eyelids (absent, mild, moderate, severe)	Decrease $\geq$ One grade
Redness of the eyelids (absent, present)	Decrease $\geq$ One grade
Redness of the conjunctiva (absent, present)	Decrease $\geq$ One grade
Conjunctival edema (absent, present)	Decrease $\geq$ One grade
Inflammation of the caruncle or plica (absent, present)	Decrease $\geq$ One grade
Subjective diplopia score  0=no diplopia; 1=intermittent (diplopia in primary position of gaze, when tired or when first awakening); 2=inconstant (diplopia at extremes of gaze); 3=constant (continuous diplopia in primary or reading position)	Decrease $\geq$ One grade
Eye muscle involvement (ductions in degrees)	Increase $\geq 8^\circ$ in at least one direction of gaze
Corneal involvement (absent/punctate keratopathy/ulcer)	Decrease $\geq$ One grade
Optic nerve involvement Best corrected visual acuity Color vision Optic disc Relative afferent pupillary defect (APD) (absent/present) Visual fields if optic nerve compression is suspected.	Change of best corrected visual acuity by $\geq$ 2 lines on Snellen chart, or substantial color vision change, or significant change of visual fields, or significant change in optic disc appearance, or (Dis-) appearance of relative afferent pupillary defect

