#### **9.6.3.1 Clinical Measures of Severity**

The Clinical Measures of Severity results (see [Table 9.3](#)) for each item will be summarized at each designated visit for each eye with the number and percentage of subjects being classified as responders on each individual criterion.

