10.6. OPTHALMIC EXAMINATION

A complete undilated ophthalmic examination will be performed as part of the physical examination. The ophthalmic exam should include best-corrected visual acuity, pupil exam, color vision assessment, Ishihara color plates (or equivalent) or related red desaturation, intraocular pressure and slit lamp exam. If significant abnormalities are noted compared with previous visits, including a loss of 2 lines or more of vision, development of pupil abnormalities including APD, rise in intraocular pressure, development of corneal infiltrates or other abnormalities not here specified but of concern to the ophthalmologist, further investigations of visual function will be conducted according to the ophthalmologist decision.

New findings reported from on-study ophthalmic examinations will not be reported as AEs if according to the investigator the abnormalities are related to TED and not related to the study drug.

For each of the assessments (pupil exam, color vision assessment, intraocular pressure, and slit lamp exam), shift tables will be presented providing the count of subjects with each type of finding (normal, abnormal - not clinically significant [NCS], or abnormal - clinically significant [CS]) at Study Baseline compared to each post-baseline visit by treatment received in HZNP-TEP-301 with percentages based on subjects with a non-missing value at the Study Baseline and post-baseline visit. In addition, a summary table will be provided for loss of 2 lines or more of vision (yes or no) including the count and percent of subjects at each post-baseline visit.

Similar summaries will be provided comparing to the HZN-001 Baseline.

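### The optic nerve severity item states no direction of benefit, so qualifying worsening from an abnormal baseline meets the response criterion

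*SAP*

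**What the plan says.** SAP Section 8.3.2.1 lists eleven Clinical Measures of Severity items. A column headed "Minimum change required for classifying overall response" says what each must do to count. Nine items require a decrease: exophthalmos, lid aperture, lid swelling, lid redness, conjunctival redness, conjunctival edema, caruncle or plica inflammation, diplopia and corneal involvement. Ductions require an increase. Optic nerve involvement is the eleventh. Its entry begins "Change of best corrected visual acuity by ≥ 2 lines on Snellen chart, or substantial color vision change", adds a significant visual field change, and ends "or significant change in optic disc appearance, or (Dis-) appearance of relative afferent pupillary defect". Protocol Table 9.3 ends its entry in the same way: "significant change in optic disc appearance, or (Dis-) appearance of relative afferent pupillary defect".

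The text below the SAP table adds four things:
- Response is judged item by item.
- A subject who has no room to improve at Study Baseline "will be considered to be a responder if they maintain the Study Baseline assessment".
- The optic nerve analysis is produced only if at least 10% of subjects have optic nerve decompression.
- A missing Week 24 evaluation counts as non-response.

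SAP Section 10.6, under safety, plans a by-visit table of subjects who lost two or more lines. It names that loss, and new pupil abnormalities including an afferent defect, among the findings that prompt further investigation.

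**The concern.** The table defines who is a responder. For every other item the stated change is a benefit. For the optic nerve, a change in either direction qualifies, and the entry expressly includes a pupillary defect that appears. Nothing else in Section 8.3.2.1 limits the entry to improvement. A programmer who codes the cell as written would therefore score deterioration as response. The same two-line loss could then count as response in an efficacy table and as harm in a safety table. At stake is whether the responder percentage for this one component can be interpreted.

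**Working it through.** The plan gives no figure to reproduce for this item, so the check is one of logic. The inputs are the optic nerve entry and the maintain rule in SAP 8.3.2.1.

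**Notation.** Let d be the change in Snellen lines (positive is a gain). Let c be the change in each of the other four elements (color vision, fields, disc, pupillary defect): +1 for qualifying improvement, 0 for no qualifying change, −1 for qualifying worsening.

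- Change criterion as written: response if |d| ≥ 2 or any c ≠ 0.
- Maintain rule, best baseline only: response if d = 0 and every c = 0. This assumes that maintaining means no change; the SAP does not define it.
- Directional criterion: response if d ≥ 2 or any c = +1, and neither d ≤ −2 nor any c = −1.

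**Results by Week 24 outcome**

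| Outcome | Abnormal baseline, as written | Best baseline, both rules apply | Best baseline, maintain rule alone | Directional criterion, with maintain rule for best baseline |
|---|---|---|---|---|
| Gain of 2 lines | Responder | Not possible | Not possible | Responder |
| Unchanged | Non-responder | Responder | Responder | Responder only if best baseline |
| Loss of 1 line only | Non-responder | Non-responder | Non-responder | Non-responder |
| Loss of 2 lines | Responder | Responder | Non-responder | Non-responder |
| New pupillary defect | Responder | Responder | Non-responder | Non-responder |

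The abnormal-baseline column needs no interpretation, because the maintain rule does not reach those subjects. The two best-baseline columns differ only in whether the maintain rule adds to the change criterion or replaces it.

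**Size of that ambiguity.** From the best baseline, allow d to be 0, −1, −2 or −3 and each of the four other elements to be unchanged or worse. That gives 4 × 2⁴ = 64 patterns.

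- Both rules apply: 63 of 64 patterns are responses. The exception is an isolated one-line loss, so a smaller loss fails where a larger one succeeds.
- Maintain rule alone: 1 of 64, the unchanged pattern.
- Directional criterion plus maintain rule: 1 of 64, the same pattern.

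These are counts of patterns, not probabilities. They show how far the two readings diverge, not how often subjects fall in each.

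**The gate.** The documents fix no sample size. For assumed totals of 30, 40, 50 and 60 subjects, 10% is 3, 4, 5 and 6 subjects.

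**The case against.** **Best-baseline subjects have their own rule.** The maintain rule exists because these subjects cannot improve, which suggests that response means improvement and that the rule replaces the change criterion for them. On that reading a two-line loss is a non-response. This is a fair reading and it stands. A reader might infer that a subject with a normal nerve is a responder whether unchanged or harmed, so that the rate in this group is fixed at its maximum. The documents do not establish that. It requires both rules to apply together, and even then an isolated one-line loss and a missing visit are non-responses. What remains is ambiguity: the rule says when such a subject responds, but not that this is the only way.

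**The row may never be produced.** Protocol 9.6.3.1 reports the "number and percentage of subjects being classified as responders on each individual criterion" without a gate, and a reader might conclude that the row appears regardless. It does not follow, because protocol 9.6 lets the SAP supersede and the SAP applies the 10% gate. Read literally as surgery, decompression would be rare: protocol 9.4.9.1 makes subjects with previous or planned TED surgery ineligible. This limits the impact. It does not change what the row means if it is produced, and the gate's own wording is uncertain, since the item refers to optic nerve compression.

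**Harm is visible elsewhere.** This is correct. SAP 10.6 provides the vision-loss table and shift tables for pupil and color vision findings, and a listing covers optic nerve scores by subject. The defect is in labelling, not concealment.

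**Improvement is obviously intended.** Probably so, and the table mock-ups, held in a separate file, may say so. The SAP text does not.

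**Conclusion.** The point holds as an error in a stated rule. For a subject with an abnormal baseline nerve, worsening past a listed threshold meets the response criterion on the plain text of both documents. For a best-baseline subject who worsens, the text supports either classification.

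The impact is limited to one descriptive component of exploratory endpoint 2; no primary or secondary endpoint uses it. The effect on the reported percentage cannot be quantified, because the documents give neither the number of subjects with an abnormal nerve nor the rates of improvement and worsening.

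Two further inferences are not supported. One is that deterioration raises the response rate among normal-nerve subjects. If both rules apply, an unchanged subject is already a responder, so qualifying worsening adds nothing to the count; if the maintain rule stands alone, worsening removes a responder. The other is that some particular share of reported responders would be deteriorations. That would need an assumed balance of improvement and worsening for which the documents offer no basis.

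**What to change.** In SAP 8.3.2.1, keep the existing thresholds and give each a direction. Response would be any of:
- improvement of best corrected visual acuity by two or more lines;
- substantial improvement in color vision;
- significant improvement in visual fields or optic disc appearance;
- disappearance of a relative afferent pupillary defect.

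The substantial and significant qualifiers should stay, since dropping them would loosen the criterion. Add one sentence saying that a subject with qualifying worsening on any element is a non-responder, including a subject with the best possible baseline. This also settles mixed cases, which the list of alternatives leaves open.

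Make the same correction in protocol Table 9.3, or record the difference in SAP Section 12. Reconcile decompression in the gate with compression in the item, so that the condition for producing the row is clear.

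The cost is one table cell, one or two sentences and a short derivation, with no new data. The downside is that the response percentage for this item may be slightly lower.
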